### 13.3.3: GIST Cohorts (Added in Update #06):

Two (2) independent phase II studies will be conducted concurrently and patients will be randomized to receive one of the two treatments. Patients will be included in the analyses according to the treatment they were randomized to.

Hypotheses: We will evaluate the confirmed response of both single agent nivolumab and dual agent nivolumab + ipilimumab. We are testing the hypothesis of a confirmed response rate being at most 5% (clinically inactive) versus a confirmed response rate of at least 20% (clinically active).

Study Design (for both treatment arms): Patient enrollment and accrual will not include those patients already enrolled to the initial cohort. We will enroll a total of 24 evaluable patients to each arm. At the time we have 9 evaluable patients, we will perform a planned interim analysis. Any demonstration of confirmed response in these 9 patients during the first 6 months of treatment allows accrual to continue. An arm demonstrating at least 3 confirmed responses during the first 6 months of treatment in 24 evaluable patients will be considered as having sufficient evidence of promising activity in this population and may be proposed for larger studies in this population.

The study will not be suspended at the time of the planned interim analysis due unless there is an unexpectedly high enrollment rate or excessive toxicity. Excessive toxicity would be 3 or more patients a month in this population.

Design Characteristics (each treatment arm): This design yields 80% power to detect a true confirmed response rate of at least 20%, with a 0.10 significance level (1-sided test) if the true confirmed response rate is 5%. There is a 64% chance of stopping early, if the true confirmed response rate is at most 5%.

## 13.4 Secondary Endpoints

- Evaluating adverse event rates (NCI CTCAE v4.0), within each study treatment arm. Categorical data analysis will be used to summarize adverse event rates and as a maximum severity during treatment for each patient and AE classification.
- Evaluating duration of response, clinical benefit rate (CBR), progression-free survival (PFS), and overall survival (OS), within each study treatment arm. Patients having PD within the first 12 weeks of starting treatment which is not a PD at their 4 week confirmation assessment will not be classified as having PD for time to event analyses. That is, estimates for response, CBR, and PD endpoints will not be censored at the first PD in such cases. Patients who are unable to continue treatment for a 4-week confirmation of PD occurring within the first 12 weeks of treatment will be counted as having PD at their first date of PD during the treatment period (eg, initial, crossover). In addition, disease assessment data beyond the date of crossover will not be included in the evaluation of the primary endpoint and for those patients crossing to dual agent treatment from single agent treatment. Such patients will be censored for estimating

duration of response, CBR, and PFS. Patients will be additionally censored at their most recent disease assessment prior to receiving any anti-cancer therapy after ending study treatment.

Kaplan-Meier methodology will be used to evaluate time to event endpoints: duration of response (time from first response to disease progression), PFS (time from randomization to the earliest of either disease progression or death from any cause), and OS (time from randomization to death from any cause). The CBR will be evaluated by counting up the number of patients with a response or stable disease (PR, CR, SD) and dividing by the total number of evaluable patients. Cumulative Incidence Function methodology may be used, as appropriate.

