### **2.2 Secondary objectives**

**2.2.1** To evaluate adverse event rates (NCI CTCAE v4.0) within each treatment arm.

**2.2.2** To evaluate duration of response, clinical benefit rate, time to progression, progression-free survival, and overall survival within each treatment arm.

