**\*Combinations of CTCAE Grade & Attribution Required for Routine AE Data Submission on Case Report Forms (CRFs)**

Attribution	Grade 1	Grade 2	Grade 3	Grade 4	Grade 5
Unrelated			a	a	a
Unlikely			a	a	a
Possible	a	a	a, b	a, b	a, b
Probable	a	a	a, b	a, b	a, b
Definite	a	a	a, b	a, b	a, b

- a) Adverse Events: Other CRF - Applies to AEs occurring between registration and within 30 days of the patient's last treatment date, or as part of the Clinical Follow-Up Phase.
- b) Adverse Events: Late CRF - Applies to AEs occurring greater than 30 days after the patient's last treatment date.

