		Respiratory, thoracic and mediastinal disorders - Other (lung infiltration)	
SKIN AND SUBCUTANEOUS TISSUE DISORDERS			
		Erythema multiforme	
	Pruritus		Pruritus (Gr 3)
Rash maculo-papular			Rash maculo-papular (Gr 3)

Adverse Events with Possible Relationship to Ipilimumab (MDX-010) (CTCAE 5.0 Term) [n= 2678]			Specific Protocol Exceptions to Expedited Reporting (SPEER)
Likely (>20%)	Less Likely (<=20%)	Rare but Serious (<3%)	
	Skin and subcutaneous tissue disorders - Other (Sweet's Syndrome)		
		Stevens-Johnson syndrome	
		Toxic epidermal necrolysis	
	Urticaria		
VASCULAR DISORDERS			
	Hypotension		

This table will be updated as the toxicity profile of the agent is revised. Updates will be distributed to all Principal Investigators at the time of revision. The current version can be obtained by contacting [contact]. Your name, the name of the investigator, the protocol and the agent should be included in the e-mail.

Ipilimumab can result in severe and fatal immune-mediated adverse events probably due to T-cell activation and proliferation. These can include (but are not limited to) autoimmune hemolytic anemia, acquired anti-factor VIII immune response, autoimmune aseptic meningitis, autoimmune hepatitis, autoimmune thyroiditis, hepatic failure, pure red cell aplasia, pancreatitis, ulcerative and hemorrhagic colitis, endocrine disorders (e.g., autoimmune thyroiditis, hyperthyroidism, hypothyroidism, autoimmune hypophysitis/hypopituitarism, and adrenal insufficiency), ocular manifestations (e.g., uveitis, iritis, conjunctivitis, blepharitis, and episcleritis), sarcoid granuloma, myasthenia gravis, polymyositis, and Guillain-Barre syndrome. The majority of these reactions manifested early during treatment; however, a minority occurred weeks to months after discontinuation of ipilimumab especially with the initiation of additional treatments.

Late bowel perforations have been noted in patients receiving MDX-010 (ipilimumab) in association with subsequent IL-2 therapy.

Complications including hyperacute graft-versus-host disease (GVHD), may occur in patients receiving allo stem cell transplant (SCT) after receiving Ipilimumab (MDX-010). These complications may occur despite intervening therapy between receiving Ipilimumab (MDX-010) and allo-SCT.

In rare cases diplopia (double vision) has occurred as a result of muscle weakness (Myasthenia gravis).

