#### *Nursing Guidelines*

- Nivolumab side effects vary greatly from those of traditional chemotherapy and can vary in severity from mild to life threatening. Instruct patients to report any side effects to the study team immediately. Side effects may be immediate or delayed up to months after discontinuation of therapy. Most side effects are reversible with prompt intervention of corticosteroids. Additionally combination therapy (with ipilimumab) tends to have a higher rate of immune mediated side effects.
- Diarrhea can be common and can be very severe, leading to colonic perforation. Instruct patients to report ANY increase in the number of stools and/or change in baseline, blood in the stool, abdominal pain to the study team immediately.
- Rash/pruritis/dermatitis is seen. Patients should report any rash to the study team. Treat per [section 8.0](#) and monitor for effectiveness.

- Monitor LFT's closely as elevations in these levels could indicate early onset autoimmune hepatitis. Patients should also be instructed to report any jaundice, or right upper quadrant pain to the study team immediately.
- Pneumonitis can be seen and may be mild (only seen on imaging) to severe. Patients should be instructed to report any SOB, dyspnea, cough, chest pain, etc. to the study team immediately. Patients reporting these symptoms should have a pulse ox checked and consider immediate imaging per the treating MD.
- Endocrinopathies (including hypopituitarism, hypothyroidism, hypophysitis, and adrenal insufficiency) are seen with this agent. Patients may present only with the vague sense of fatigue and "not feeling well". Additional symptoms may be that of nausea, sweating and decreased activity tolerance. Instruct patients to report these signs or symptoms immediately and obtain appropriate labs as ordered by MD.
- Pancreatitis is possible with nivolumab. Instruct patients to report abdominal pain, nausea and vomiting to the study team.
- Patients who are started on steroid therapy for any side effects of nivolumab toxicity should be instructed to take the steroids as ordered, and not to discontinue abruptly as symptoms may return and be severe. Patients may be on steroid therapy for weeks. Instruct patients to report any increase or change in side effects with any dosage decrease as patients may need a slower taper

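### Section 13.4 summarizes adverse events by worst grade in an undefined on-treatment window, so delayed drug-related events that the protocol expects and collects may be left out

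*Combined protocol and SAP*

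**What the plan says.** Secondary objective 2.2.1 is "To evaluate adverse event rates (NCI CTCAE v4.0) within each treatment arm". It has no time limit. The analysis rule for it is one sentence in Section 13.4, under which categorical methods will be used to "summarize adverse event rates and as a maximum severity during treatment for each patient and AE classification". Neither that section nor any other says when treatment ends for this purpose, or whether events reported after treatment enter the table.

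On timing, the Nursing Guidelines for nivolumab (10.2) and for ipilimumab (10.3) carry the same warning: "Side effects may be immediate or delayed up to months after discontinuation of therapy". Footnote 2 of the ipilimumab risk list (9.4.2) says of immune-mediated reactions that "a minority occurred weeks to months after discontinuation of ipilimumab especially with the initiation of additional treatments".

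On collection, Section 9.2 uses two forms. The Other form runs from registration to 30 days past the last treatment and also takes events from clinical follow-up. The Late form "Applies to AEs occurring greater than 30 days after" the last treatment, and the table marks it only for grades 3 to 5 with possible, probable or definite attribution. The study calendar (5.0) requires an adverse-event assessment 4 weeks after treatment ends, give or take 7 days. It stops solicited collection once a patient is off treatment.

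**The concern.** The protocol expects some drug-related toxicity after dosing ends and has forms to record it, but the stated summary rule does not clearly use those records. Exposure also outlasts dosing: the terminal half-lives given in Section 10 are 25.6 days for multiple-dose nivolumab and 14.7 days for ipilimumab.

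The AE stopping rule in Section 13.7 counts at least possibly related grade 3 or higher events and places no on-treatment limit on them. A related grade 3 hepatitis that starts two months after the last dose could therefore count toward suspending accrual and yet be missing from the reported severity table.

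At stake is a secondary endpoint. The per-arm rates of grade 3 or higher events are what a reader would weigh against response when deciding whether either regimen should go to a larger study.

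**Working it through.** The plan states no adverse-event rate for this trial, so there is no figure to reproduce. The check has three steps.

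**1. What each window would capture**

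| Onset of event | Where recorded (9.2) | In the 13.4 summary? |
|---|---|---|
| While on treatment | Solicited form; Other form | Yes |
| After treatment, to 30 days | Other form (grades 1-2 if at least possibly related; grades 3-5 any attribution) | Not stated |
| After 30 days | Late form (related grades 3-5 only); Other form if part of clinical follow-up | Not stated; excluded if read literally |

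**2. Direction.** Let M1 be a patient's worst grade in the on-treatment window and M2 the worst grade in any longer window that contains it. Then M1 ≤ M2 for every patient. The proportion with grade 3 or higher under M1 is therefore equal to or below the proportion under M2. The restriction cannot push the rate up.

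**3. Size.** Let f be the share of an arm's patients whose only grade 3 or higher related event falls outside the window. The restricted rate is the full rate minus f. The documents do not give f, so the values below are assumptions. With n evaluable patients per arm (38 in 13.3.1, 12 in 13.3.2, 24 in 13.3.3), the expected number missed is n × f. Treating patients as independent, the chance of missing at least one is 1 − (1 − f)^n.

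| n | f = 1% | f = 2% | f = 5% | f = 10% |
|---|---|---|---|---|
| 12 | 0.12; 0.11 | 0.24; 0.22 | 0.6; 0.46 | 1.2; 0.72 |
| 24 | 0.24; 0.21 | 0.48; 0.38 | 1.2; 0.71 | 2.4; 0.92 |
| 38 | 0.38; 0.32 | 0.76; 0.54 | 1.9; 0.86 | 3.8; 0.98 |

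Each cell gives the expected number missed, then the chance of at least one. At f = 0 nothing changes. For example, with n = 24 and f = 5%: 24 × 0.05 = 1.2, and 1 − 0.95^24 = 0.71.

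One missed patient moves an arm's rate by 1/38 = 2.6, 1/24 = 4.2 or 1/12 = 8.3 percentage points.

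**The case against.** **The sentence may describe two summaries.** It can be read as adverse-event rates with no window, plus a separate maximum-severity table. That reading is fair. The window for the rates is then unstated and still has to be written down.

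**'During treatment' may be meant to include 30 days.** Events to that point share the Other form with on-treatment events, so they are not set apart by form. This stands: only the Late form is separate. It does not settle what happens to Late-form events.

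**Most toxicity is early.** The ipilimumab footnote says "The majority of these reactions manifested early during treatment". In addition, most categories in Section 8.2.2 take patients off therapy at grade 3 or 4, and such patients have usually already entered the overall grade 3 or higher count. This limits the loss in a patient-level rate. It helps less in tables by event type, where a later event of another type is still lost.

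**Collection after treatment is uneven.** Solicited terms stop, only related grade 3-5 events are marked for the Late form, and after progression the calendar asks for survival information every 6 months. An on-treatment table with uniform collection is a defensible main summary. This stands, and is why that table should be kept and a second one added.

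**Patient protection does not depend on this table.** The stopping rule and expedited reporting operate separately. Agreed; the point is about reported rates.

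**Stronger readings that a reader might infer.** One is that the rates will be understated. The documents do not show it, since they give no late-only share. Another is to discount the 43% (Section 1.6) or 53% (Section 1.5) grade 3-4 rates for the combination. Those come from renal-cell and melanoma studies, the 43% pools two dose regimens, and the observation window behind neither is given. They are not estimates for this trial. A third is that symptoms present at baseline inflate the counts. That is a separate reporting choice with the opposite direction; Section 13.4 does not say that baseline grades are ignored, and Section 9.1 provides a baseline form.

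**Conclusion.** The point holds as a gap in the stated rule. The window in Section 13.4 is undefined and, read literally, omits post-treatment events that the protocol both anticipates and records. Rates of grade 3 or higher events may be understated. The window cannot overstate them. The amount is unknown: under an assumed late-only share of 0 to 10% of patients, the shortfall is 0 to 10 percentage points, or 0 to 3.8 patients expected in the largest arm. The range illustrates scale and is not a forecast. It takes the evaluable patients as the denominator. The primary endpoint and the stopping rule are not affected. The change is worth making before the final safety tables are produced.

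**What to change.** In Section 13.4:

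- Keep the on-treatment summary of all grades and define its window as first dose to 30 days after last dose. Note that solicited terms are collected only until the patient goes off treatment.
- Add each patient's maximum severity of at least possibly related grade 3-5 events from first dose through all reported follow-up, using the Other and Late forms together.
- Tabulate onset on treatment, within 30 days, and after 30 days.
- Show events after the start of other anti-cancer therapy in a separate column. Dropping them would remove some of the late reactions that the ipilimumab footnote links to further treatment. Show events after crossover from Arm 1 separately as well.
- State that required collection after 30 days covers only at least possibly related grade 3-5 events, so the extended summary is not complete for lower grades or unrelated events.

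The cost is a few sentences and a table program. No new data are needed: both forms exist, and the dates of crossover and other therapy are already required by the censoring rules in 13.3 and 13.4. The trade-offs are possibly slightly less favorable high-grade rates and a second table that rests on less complete follow-up than the first.

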- C Every 6 weeks for 12 weeks, then every 8 weeks until evidence of progression or relapse. Scans may be performed +/- 7 days from scheduled date. During the first 12 weeks of therapy, patients can be considered for continuation of treatment (see [Section 7.1](#) for further details and footnote D below). Confirmatory scans to be obtained at least 4 weeks following documentation of objective response (see [Section 11.0](#)). Response assessment should include assessment of all sites of disease and use the same imaging method as was used at baseline. For patients receiving initial treatment beyond 2 years from randomization date; scans may be performed every 3 months for year 3, every 4 months for year 4, every 6 months for year 5 and then yearly thereafter. One confirmatory scan continues to be required if patient achieves a response for the first time and during this period. Thereafter, returning to the assessment schedule.
- D If there is evidence of progression in the first 12 weeks, treatment is allowed to be continued. The patient's baseline assessment is now the 1st assessment showing progression (not the pre-study disease assessment) and is used for the remainder of the patient's initial treatment assignment (not crossover). Contact the Data Manager or Study Chair for questions. If this occurs, an additional scan is to be scheduled 4 weeks from the regular scan (i.e. at week 10 or 16). Thereafter, the patient will have a scan every 8 weeks. See also [section 7.1](#) for further information.
- E. **Crossover Patients Only:** For patients who crossover to dual agent therapy, a baseline scan is required  $< 28$  days prior to re-registration. After initiation of dual agent therapy scans are every 6 weeks for 12 weeks, then every 8 weeks until evidence of progression or relapse (scans may be done +/- 7 days from due date). During the first 12 weeks of therapy, patients can be considered for continuation of treatment (see [Section 7.1](#) for further details and footnote D above with the appropriate reset for baseline disease measurement. Contact the Data Manager or Study Chair for questions). Confirmatory scans are to be obtained at least 4 weeks following documentation of objective response (see [Section 11.0](#)). Response assessment should include assessment of all sites of disease and use the same imaging method as was used at the baseline measurements associated with crossover. For patients receiving crossover

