## 7.1 Treatment Decisions within the First Twelve Weeks of Therapy

Note: This section is applicable to initial treatment assignment, and to patients who are crossing over from the single agent nivolumab to combination treatment.

Patients who progress by imaging (See [Section 11.4.3.2](#)) during the first 12 weeks of therapy may continue treatment, at the discretion of the patient and treating investigator. These patients must meet all of the following in order to be eligible to continue therapy:

- No more than 4 new lesions. The sum of the longest diameter (SHORT diameter for LN) of target lesions and the new lesions are less than 40% increase from the baseline.
- Patients must be clinically stable with no change in performance status due to disease progression
- No indication for immediate alternative treatment
- Patient [assessed by the investigator] is showing clinical benefit and tolerates study drug. The assessment of clinical benefit should take into account whether the subject is clinically stable or deteriorating and likely or unlikely to receive further benefit from continued treatment.
- The time of progression is noted from the first assessment that exceeds standard criteria

New lesions are considered measurable at the time of initial progression if the longest diameter is at least 10 mm (except for pathological lymph nodes, which must have a short axis of at least 15 mm). Any new lesion considered non-measurable at the time of initial progression may become measurable and therefore included in the tumor burden measurement if the longest diameter increases to at least 10 mm (except for pathological lymph nodes, which must have an increase in short axis to at least 15 mm).

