If the decision is made to continue treatment after progressive disease is identified within the initial 12 weeks (and criteria above are met), then the patient may continue therapy for a maximum of 4 weeks. **Note:** At this time, the baseline scan to use for further assessments of disease status is reset to this assessment. After 4 weeks a scan is to be repeated. If the scan shows progression compared to the scan 4 weeks prior, they should be removed from protocol therapy. If the scan shows stable disease or response, compared to the scan 4 weeks prior, they can remain on protocol therapy should they choose to and the suspected initial progression date and assessment is considered the baseline scan to use for until further PD is evident. See section [11.4.3.2](#) for more information for determining objective status and [section 12.1](#) for information regarding duration of therapy. Scan schedule will resume routine schedule, as per [Section 5.0](#) footnote D.

Patients who have progression AFTER the initial 12-week period will be removed from protocol therapy in arm 2 (arm 1 patients may elect to cross over to dual agent therapy with progression after a minimum of 10 weeks of single agent nivolumab).

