### 11.1 Schedule of Evaluations:

**Initial Treatment (Assigned at Registration/Randomization):** For the purposes of this study, patients should be evaluated every 6 weeks for 12 weeks, and then every 8 weeks thereafter. In addition to a baseline scan, confirmatory scans should also be obtained 4 weeks following initial documentation of objective response. See [Section 7.0](#) for further details. Additionally, see [Section 7.1](#) for instructions for how to treat, rescan, and use the proper disease assessment (e.g. baseline, reset baseline, or crossover baseline) for comparison in patients who demonstrate progressive disease within the first 12 weeks of study participation. For patients receiving initial treatment beyond 2 years from randomization date; scans may be performed every 3 months for year 3, every 4 months for year 4, every 6 months for year 5 and then yearly thereafter. One confirmatory scan continues to be required if patient achieves a response for the first time and during this period. Thereafter, returning to the assessment schedule.

**Crossover Treatment:** Patients having crossed over to dual agent therapy following progression of disease while receiving single agent nivolumab (per [section 3.4](#)) should be evaluated every 6 weeks for 12 weeks, and then every 8 weeks thereafter. As per [section 5.0](#), patients must have imaging performed within 28 days of re-registration to dual agent therapy. This scan will be the baseline scan for patients to determine response to dual agent therapy. For patients receiving crossover treatment beyond 2 years from date of crossover, scans may be performed every 3 months for year 3, every 4 months for year 4, every 6 months for year 5 and then yearly thereafter. One confirmatory scan continues to be required if patient achieves a response for the first time and during this period. One confirmatory scan continues to be required if patient achieves a response for the first time and during this period. Thereafter, returning to the assessment schedule.

See [Section 7.0](#) for further details. Additionally, see [Section 7.1](#) for instructions for how to treat, rescan, and use the proper disease assessment for comparison for patients who demonstrate progressive disease within the first 12 weeks of study participation.

In all cases, supporting documentation of response and progression should be submitted, per [Section 6.1.1](#).

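### An early PD is dropped from PFS and CBR on a scan read against the progression scan, so a tumour still in RECIST v1.1 progression can lose its first PD date

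*Combined protocol and SAP*

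**What the plan says.** Section 13.4 sets the rule for the secondary endpoints: patients with a PD in the first 12 weeks "which is not a PD at their 4 week confirmation assessment will not be classified as having PD for time to event analyses". Patients who cannot continue to the 4-week scan keep their first PD date. Section 13.4 does not itself name the scan against which the 4-week scan is read.

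Other sections do. Section 7.1 says that after an early PD "the baseline scan to use for further assessments of disease status is reset to this assessment", and of the repeat scan: "If the scan shows stable disease or response, compared to the scan 4 weeks prior, they can remain on protocol therapy". Footnote D of the Study Calendar makes the new baseline the first "assessment showing progression (not the pre-study disease assessment) and is used for the remainder of the" patient's initial treatment. Section 11.1 tells readers to "use the proper disease assessment (e.g. baseline, reset baseline, or crossover baseline) for comparison in patients who demonstrate progressive disease" in the first 12 weeks, and the notes in 11.3.3 to 11.4.4 refer back to 11.1.

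Two other statements bear on dates. A bullet in 7.1 reads: "The time of progression is noted from the first assessment that exceeds standard criteria". On later scans, footnote D says "Thereafter, the patient will have a scan every 8 weeks", while 7.1 says "Scan schedule will resume routine schedule, as per" and then cites that same footnote.

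Section 13.3 uses the same confirmatory scan for the primary endpoint: an early PD that is not confirmed leaves the patient evaluable, and later cycles count towards response. Section 13.1 says the primary endpoint is evaluated by RECIST v1.1.

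**The concern.** The purpose of looking past an early PD is to avoid counting growth that later reverses. The rule as assembled from 13.4 and 7.1 does not test for reversal. It asks only whether the tumour grew a further 20% in the four weeks after progression. A tumour that stays at its progressed size, or keeps growing more slowly, passes as readily as one that shrinks back.

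PFS and CBR would then be more favourable than under standard RECIST v1.1 dating, and a reader told that RECIST v1.1 was used would not know it. Section 7.1 compounds this by dating progression from the first scan that crosses the standard threshold, which is the date 13.4 discards. The bullet can be read as covering confirmed PD only, but neither section says so, and two analysts could derive different PFS from the same data.

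**Working it through.** The plan gives no event count, power or target for PFS or CBR, so there is no planned figure to reproduce. The check applies the plan's own thresholds.

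**Inputs**
- PD: at least 20% (and 0.5 cm) above the minimum sum (11.4.3.2).
- PR: at least 30% below the baseline sum (11.4.3.2).
- Limit on continuing after early PD: less than 40% above baseline (7.1).
- Scans at weeks 6 and 12; extra scan 4 weeks after an early PD, at week 10 or 16; then every 8 weeks (footnote D).
- Evaluable patients per arm: 38 (13.3.1), 12 (13.3.2), 24 (13.3.3).

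**Assumptions**: pre-study sum 100, no earlier shrinkage, the 0.5 cm condition met, target lesions only, all 7.1 conditions met, nominal scan weeks counted from randomization.

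**Step 1: 4-week sums that erase the first PD.** The continuation limit puts the progression scan at 120 to 139. The 4-week scan is not PD against the reset baseline if it is below 1.2 × the reset sum:
- 1.2 × 120 = 144
- 1.2 × 139 = 166.8

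Sums from 120 up to those caps are still PD against the pre-study scan. For example, 100, then 125, then 137.5 is +37.5% on pre-study but 137.5/125 = +10% on the reset baseline, so the first PD is dropped. An unchanged 125 is dropped as well.

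**Step 2: timing under steady growth.** Let g be the growth factor per 6 weeks.
- First PD at week 6 within the limit: 1.20 ≤ g < 1.40. Week 10 is not PD if g^(4/6) < 1.2, i.e. g < 1.2^1.5 = 1.3145. The week-10 sum is then 135.5 to 157.7. Week 18 over reset = g² = 1.44 to 1.73, which is PD. The event moves from week 6 to week 18. For g from 1.3145 to 1.40 the PD is confirmed at week 10 and nothing moves.
- First PD at week 12 within the limit: 1.20 ≤ g² < 1.40, so g = 1.0954 to 1.1832. The 4-week factor is 1.063 to 1.119, never PD; the week-16 sum is 127.5 to 156.6. Week 24 over reset = g² = 1.20 to 1.40, which is PD. The event moves from week 12 to week 24.

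**Step 3: landmarks.** Three months is about week 13.0 and six months about week 26.1. Weeks 18 and 24 both lie between them, so 3-month PFS rises and 6-month PFS does not. Each affected patient adds 1/n, absent earlier censoring: 1/12 = 8.3 points, 1/24 = 4.2, 1/38 = 2.6.

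If the original routine weeks (12, 20, 28) were kept instead:
- A week-6 PD moves only to week 12, since week 12 over reset = g ≥ 1.20.
- A week-12 PD moves to week 20 if g^(8/6) ≥ 1.2, i.e. g ≥ 1.2^0.75 = 1.1465 (reset sum 131.5); otherwise to week 28. Only these week-28 cases move 6-month PFS.

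Start delays and scan windows can shift these nominal weeks relative to either landmark.

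**Step 4: CBR.** Section 11.3.3 requires SD at least once, at a minimum of 6 weeks after study entry. A week-6 progressor whose week-10 scan is SD against the reset baseline meets that. A week-12 progressor who was stable at week 6 already counted, so only week-6 progressors add to CBR.

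**Step 5: primary endpoint.** After a reset, PR needs 0.7 × the reset sum:
- 0.7 × 120 = 84, which is 16% below pre-study
- 0.7 × 139 = 97.3, which is 2.7% below pre-study

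**The case against.** Treating past early PD and resetting the baseline are deliberate choices for checkpoint inhibitors, and footnote D expressly excludes the pre-study scan. PFS and CBR carry no decision rule, and the arms are not compared. Sampling error is also large: assuming 3-month PFS near 30%, the 95% half-width is 1.96 × √(0.3 × 0.7/n), about 26 points at n = 12 and 15 at n = 38. All of this stands. It limits the consequence but does not remove the one-directional shift or the undisclosed departure from RECIST v1.1.

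A reader might go further in five ways that the documents do not support.
- That the comparator is undefined. It is not repeated in 13.4, but 7.1, footnote D and 11.1 supply it.
- That the scan schedule is an open conflict. The 7.1 sentence resumes the routine schedule by citing footnote D, which says 8-weekly. The wording is loose; the 8-weekly reading is the better supported.
- That 6-month PFS is inflated. In this model that needs the original routine weeks, a first PD at week 12 and a reset sum below 131.5.
- That a few re-dated patients would carry an arm from the inactive to the active PFS benchmark in Section 1.1 (21% versus 39% at 3 months, 8% versus 14% at 6). Those trials used WHO criteria, Section 13 does not use them as a comparator, and the number re-dated is unknown. They are context only.
- That an early PD should be dropped only if it reverses against the pre-study scan. That would override the stated design and add a third PFS definition.

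**Conclusion.** The concern holds as a matter of definition and reporting. Under the plan as written, a tumour up to 44 to 66.8% above its pre-study sum can lose its first PD date. With steady growth on footnote D's schedule the event is delayed by 12 weeks, not abolished; in practice a death or a censoring may come first. The effect is at most 8.3, 4.2 or 2.6 points of 3-month PFS per affected patient at n = 12, 24 or 38, with a possible gain in CBR for week-6 progressors and no change in 6-month PFS in this model. The same reset lets a confirmed response be counted at a sum 2.7 to 16% below pre-study.

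Only patients who meet the 7.1 continuation conditions are affected, and the documents do not allow their number to be derived. The result is therefore a direction and a size per patient, not an estimated bias. It would be tempting to say that the primary decision is compromised; the documents do not show that any response would depend on the reset. They do show that the 13.4 rule and the 7.1 dating bullet need to be reconciled, and that the RECIST v1.1 label in 13.1 needs qualifying.

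**What to change.** Change the analysis text only; treatment rules stay as they are.

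1. Keep the planned reset-baseline analysis. State in 13.3 and 13.4 that the comparator for the 4-week and later scans is the reset baseline, and that this departs from standard RECIST v1.1. Reconcile 13.4 with the 7.1 dating bullet by saying whether that bullet covers confirmed PD only.
2. Report PFS and CBR with PD dated at the first RECIST v1.1 PD alongside the planned version.
3. Report a sensitivity count of confirmed responses measured against the pre-study baseline, where the pre-study target lesions remain traceable.
4. As a minor clarification, align the wording on scans after the extra scan in 7.1 and footnote D.

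Items 1 and 4 cost only wording. Item 2 needs a date that 7.1 already has noted. Item 3 needs pre-study target lesions to stay identifiable after the reset, which the documents do not state. The price is somewhat less favourable PFS and CBR and a possibly lower sensitivity response count. The RECIST version also counts pseudoprogression as PD, which is why both versions should be shown.
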